10 SOURCE DOCUMENTS AND ACCESS TO SOURCE DATA/DOCUMENTS		
.....	11	11 ETHICS/PROTECTIONI OF HUMAN
SUBJECTS.....	12	
11.1 Consent Procedures and Documentation	12	
11.2 Participant and Data Confidentiality	13	
12 DATA HANDLING AND RECORD KEEPING	13	
12.1 Study Records		
Retention	14	
12.2 Protocol Deviations	15	
14 SCHEDULE OF EVENTS.....	16	

LIST OF ABBREVIATIONS

AE	Adverse Event/Adverse Experience
CFR	Code of Federal Regulations
CRF	Case Report Form
DCC	Data Coordinating Center
DHHS	Department of Health and Human Services
DSMB	Data and Safety Monitoring Board
GCP	Good Clinical Practice
HIPAA	Health Insurance Portability and Accountability Act
ICF	Informed Consent Form
ICH	International Conference on Harmonisation

IRB	Institutional Review Board
MOP	Manual of Procedures
N	Number (typically refers to participants)
OHRP	Office for Human Research Protections
PI	Principal Investigator
POD	Postoperative day
SAE	Serious Adverse Event/Serious Adverse Experience
SOC	Standard of Care
STSG	Split Thickness Skin Graft
UP	Unanticipated Problem

Study number: s19-00437

Version: 3.2

PROTOCOL SUMMARY

Title	Impact of Promogran Prisma™ on pain of split-thickness skin graft donor sites compared to standard of care alone – a pilot study
Short Title	Impact of Prisma on donor site pain
Brief Summary	Twenty patients will be randomized into two groups: control and treatment. The control group will receive standard of care (SOC) dressings at the split thickness skin graft (STSG) donor site and the treatment group will receive Promogran in direct contact with the donor site in addition to SOC. SOC at NYU Winthrop Hospital includes, but is not limited to, xeroform or semi-occlusive adhesive dressings. The primary outcome is to assess the feasibility of evaluating Promogran in addition to SOC for the management of donor-site pain following STSG. The only difference between the two groups is the addition of Prisma in direct contact with the donor site under the SOC dressings in the treatment group.
Objectives	The primary objective of this study is to assess the feasibility of evaluating the use of a composite collagen, silver-oxidized regenerated cellulose matrix compared to the standard of care dressing on donor site pain for patients undergoing split-thickness skin grafting in preparation for a larger study.
Methodology	This is a prospective, randomized, open-label, single-center feasibility study.
Endpoint	The primary endpoint of this feasibility study is to evaluate if using Promogran in addition to SOC is associated with a clinically meaningful difference in pain score (≥ 2 points on the visual analog pain scale) between the treatment and control arms on postoperative day (POD) 1.
Study Duration	Two years
Participant Duration	Six weeks
Duration of IP administration	One application
Population	Twenty patients; 10 in the intervention group and 10 in the control group. All genders, ≥ 18 years old, all demographics and geographic locations; scheduled to undergo STSG.
Study Sites	Single site: NYU Winthrop Hospital
Number of participants	20 participants
Study compensation	\$70. Two payments of \$35 will be given to participants – one at enrollment and one at collection of the 10-day pain diary.
Description of Study Agent/Procedure	Promogran Prisma™ is a composite collagen-silver-oxidized regenerated cellulose dressing that is a sheet applied topically to the STSG donor site.
Reference Therapy	The control group will receive a standard of care dressing on the STSG donor site (i.e., non-adherent dressing)
Key Procedures	Placement of either Prisma or standard of care dressing on the STSG donor site. Record daily pain score of the donor site for 10 days post-grafting. Return to clinic for weekly follow-up visits for 6 weeks.

Statistical Analysis	Proposed sample size (10 patients in each arm, a total of N=20) is obtained from a recruitment and cost feasibility point of view. For the primary endpoint, the pain score at POD 1 will be compared between treatment groups using Wilcoxon rank-sum (Mann-Whitney) test. The secondary endpoint, time from randomization to donor site healing, will be compared between treatment groups using time to event approach via Kaplan-Meier method.
----------------------	--

SCHEMATIC OF STUDY DESIGN

Total 20: Obtain informed consent. Screen potential subjects by inclusion and exclusion criteria. Perform physical examination and review medical, surgical, and medication histories. Perform a urine pregnancy test for females of reproductive potential. Collect (Day -7 - 0) demographic data including: date of birth, gender, race, ethnicity and tobacco use.

2.1 Background Information and Relevant Literature

Split-thickness skin grafting (STSG) is the mainstay of therapy for the management of wounds that cannot be closed primarily or left open to close by secondary intention. However, the wounds created by STSG are often a source of pain and morbidity to patients. Multiple studies have compared various donor site dressings in attempt to decrease pain and morbidity¹⁻⁴. This study will look specifically at the effect on patient-reported donor site by using of a collagen dressing. The addition of a composite collagen-silver-oxidized regenerated cellulose dressing (Promogran Prisma™) which has been cleared by the FDA(510k) in direct contact with the donor site is hypothesized to decrease pain at the donor site.

2.2 Potential Risks & Benefits

Risks involved with the procedures (i.e. surgical procurement of the STSG, use of advanced wound care therapies included in the SOC at NYU Winthrop Hospital Wound Center) are similar to risks in the standard treatment of wounds of this nature (i.e. infection; allergic reaction; excessive redness, pain, swelling, or blistering). Procurement of the STSG will be performed under sterile conditions in the operating room under monitored supervision and adequate pain control by a trained anesthetist. There is no difference between the treatment and control groups in the way that the STSG is obtained. Standard risks associated with anesthesia will be explained to the patient in detail prior to the operation. Skin grafting can cause localized pain with associated local bleeding that will be controlled in the operating room.

Benefits include decreased pain at the STSG donor site, decreased time to heal, and decreased occurrence of adverse events (e.g. wound infection). Even in the event that no improvement is made to donor site pain or wound healing, information gained from the study will be used to help understanding and improve future treatment options for people undergoing STSG.

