5 STUDY ENROLLMENT AND WITHDRAWAL

Participants will be recruited from the NYU Winthrop Hospital Wound Care center, inpatient service, and other outpatient surgical services. Consent will be obtained by the principal and sub-investigators of the study.

5.1 Randomization:

Randomization will be performed 1:1 at enrollment. A computer generated randomized block assignment list will be given to the study coordinator. Each block of 2 or 4 subjects will contain an equal number of the two groups: 1) SOC, 2) Promogran+SOC. SAS PROC PLAN will be used to generate this list.

5.2 Inclusion Criteria:

1. Patient ≥ 18 years of age
2. Male or female
3. Patient scheduled to undergo STSG for any reason
4. Patient is able to provide informed consent and has read and signed the IRB-approved informed consent form.

5.3 Exclusion Criteria:

1. Active infection or history of radiation to the donor site
2. Patient has a known sensitivity to Promogran Prisma™ or silver
3. Elevated INR >3.0
4. Insensate at the donor site
5. Chronic narcotic use (>6 months of daily use)
6. Patient is currently pregnant and/or breastfeeding

The target number of enrolled patients will be 20, with 10 patients in the control and treatment groups, respectively. Patients will be allowed to withdraw consent at any time, with no adverse effect on the care received at NYU Winthrop Hospital.

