6 STUDY PROCEDURES AND SCHEDULE

The study will last six weeks. After consent and enrollment, patients in both the control and treatment groups will undergo STSG as scheduled. Promogran will be available in the operating room and applied by the operating surgeon (study or non-study surgeon) directly to the donor site of patients randomized to the treatment group. Patients in the control group will receive SOC dressings per the attending surgeon's clinical judgment. SOC dressings include a primary non-adherent dressing, a secondary gauze and transparent film or tape. The only difference between the two groups is the addition of Prisma in direct contact with the STSG donor site under the primary dressing in the treatment group.

Pain will be patient-reported using the visual analogue/Wong-Baker pain rating scale (VAS), which is reported on a scale from 0-10. Pain will be measured once at each of the following 12 time points: preoperatively, post-operatively (POD 1), and each subsequent postoperative day for ten days. After day 10, pain will be recorded by the assessing clinic provider during the weekly visits, until week six.

Patients will be followed daily while inpatient and weekly while outpatient for six weeks. The number of study visits will be between 6-10. The study visits will be combined with SOC visits and there will

be no study related procedures other than assessing pain at the donor site. Dressings will be changed and wounds assessed according to the standard of care at NYU Winthrop Hospital.

Screening Phase - Week -1 (within 7 days prior to treatment visit)

- Evaluation of eligibility for study inclusion
- Obtain informed consent
- Screening of inclusion/exclusion criteria
- Assign a unique subject identification number (SID).
- Randomize to treatment or control arm
- Perform physical examination and review medical, surgical, and medication histories.
- Perform a urine pregnancy test for females of reproductive potential.
- Collect demographic data including: date of birth, gender, race, ethnicity and tobacco use.
- Give patient pain diary and payment of \$35 patient stipend.

Treatment Phase - Day 0

- Ensure subject remains eligible prior to study product application.
- Confirm negative urine pregnancy test for females of reproductive potential prior to initial product application.
- Application of Prisma to STSG donor site for patients in the treatment group □ Record STSG donor site length and width

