- Records all pain medications used in postoperative recovery room on POD 0

Follow-Up – Day 1 to 10

- Daily record of pain level in pain journal with the initial record once during 8am to 12pm and prior to each pain medication use
- Record time of any pain medication use
- Record pain of both donor and recipient STSG site

Follow-Up - Weeks 1 to 6 (6 week duration with 1 visit per week)

- Evaluation and record of STSG donor site – photography, length, width
- Record pain level of donor site
- Record any adverse events
- Collection of pain diary and second payment of \$35 stipend.

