14 SCHEDULE OF EVENTS

Activity	Screening Visit [Day -7-0]	Treatment Visit [Day 0]	Follow-Up Phase [Day 1-10]	FollowUp Visit 1 [Day 7±3]	Follow-Up Visit 2 [Day 14±3]	Follow-Up Visit 3 [Day 28±3]	Follow-Up Visit 4 [Day 35±3]	Follow-Up Visit 5 [Day 42 ±3]	Final Visit 6 [Day 49 ±3]
Informed Consent	X								
Eligibility Assessment	X								
Significant Medical, Surgical, Medication History	X								
Baseline demographics: gender, age, height, weight	X								
Pain score at STSG donor site	X	X	X	X	X	X	X	X	X
Randomization		X							
Application of Promogran Prisma™, for intervention group		X							
STSG donor site evaluation and management (SOC dressing, photography, length, width, assessment of appearance)				X	X	X	X	X	X
Closure assessment				X	X	X	X	X	X

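### The arm can be known before the graft is taken, and the planned data hold no graft thickness or named donor-site location, so comparable harvest is neither protected nor checkable from them

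*Combined protocol and SAP*

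**What the plan says.** **Harvest.** Section 2.2, on risks and benefits, says "There is no difference between the treatment and control groups in the way that the STSG is obtained". Section 6 adds that "After consent and enrollment, patients in both the control and treatment groups will undergo STSG as scheduled". No section describes a harvest technique or a graft thickness. Section 5.2 admits grafting for any indication, and Section 6 allows the operator to be a study or a non-study surgeon.

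**Timing and knowledge of the arm.** Section 5.1: "Randomization will be performed 1:1 at enrollment". Section 6 lists "Randomize to treatment or control arm" in the screening phase, which covers the 7 days before the treatment visit. Section 14 places randomization at the Day 0 treatment visit. The Protocol Summary (Methodology) says "This is a prospective, randomized, open-label, single-center feasibility study".

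**Donor-site data.** On Day 0, Section 6 asks staff to "Record STSG donor site length and width". At the weekly visits it asks for "Evaluation and record of STSG donor site – photography, length, width". The schedule in Section 14 adds appearance, and Section 4.2 adds granulation in quartiles.

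**Analysis.** Section 9.3 compares POD 1 pain by the Wilcoxon rank-sum test. It adds an ANCOVA with baseline pain and any baseline variable that is unbalanced or correlates with outcome above 0.30. Section 9.4 compares healing by Kaplan-Meier curves and the log-rank test, without covariates.

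**The concern.** The harvest creates the wound whose pain and healing are the outcomes. If the surgeon can know the arm before cutting, an influence on the outcome is fixed after assignment and without concealment. The plan then keeps no record by which anyone could see whether the two arms were harvested alike.

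Two consequences need to be kept apart. A difference in thickness arising by chance adds noise, which the trial could partly remove if thickness were recorded. A difference arising because the arm was known would be bias, and would not shrink in a larger trial. Section 9.1 bases no decision on p-values, but it treats the direction and size of the observed effect as critical for designing the next trial, so a distorted estimate would carry forward.

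**Working it through.** **1. When can the arm be known?**
- Section 5.1: at enrollment, hence before surgery.
- Section 6: in screening, up to 7 days before the treatment visit.
- Section 14: Day 0, with no order relative to harvest.
- No section withholds the arm until the graft has been taken.

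The three places disagree on the day, but none puts assignment after harvest.

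**2. Can the planned data show that harvest was comparable?** The listed items are length, width, photographs, appearance and granulation. Thickness and instrument setting are absent. Location has no named field, though photographs may show it. Section 10 counts hospital records as source documents but names no harvest item for extraction.

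**3. Can the analysis adjust for it?** The rule in Section 9.3 can act only on a recorded variable. The healing analysis in Section 9.4 has no covariates. So neither outcome can be adjusted for thickness.

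**4. Scale.** The plan has no power calculation to reproduce; its only figure here, 10 + 10 = 20, agrees. Inputs: n = 10 per arm (Section 9.1) and 2 points as the difference of interest (Section 4.2). Pain SD of 2 to 3 and thickness-pain correlation r of 0.3 to 0.5 are assumptions; the documents give neither.

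- Standard error of a between-arm difference in any variable, in SD units: sqrt(2/10) = 0.447.
- P(|difference| > 0.5 SD) = P(|Z| > 1.118) = 0.264. P(|difference| > 1 SD) = P(|Z| > 2.236) = 0.025.
- Shift in the pain contrast = r × imbalance × SD.
  - Imbalance 0.5 SD: 0.3 × 0.5 × 2 = 0.30 to 0.5 × 0.5 × 3 = 0.75 points, or 15% to 38% of 2 points.
  - Imbalance 1 SD: 0.3 × 1 × 2 = 0.6 to 0.5 × 1 × 3 = 1.5 points, or 30% to 75% of 2 points.
- Standard error of the pain contrast = SD × 0.447 = 0.89, 1.12 and 1.34 at SD 2, 2.5 and 3. A 0.5 SD imbalance therefore moves the contrast by 0.3 × 0.5/0.447 = 0.34 to 0.5 × 0.5/0.447 = 0.56 of one standard error.
- Adjustment would multiply that standard error by sqrt(1 − r²): 0.954 at r = 0.3 and 0.866 at r = 0.5, before the small loss of degrees of freedom.

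The probabilities 0.264 and 0.025 hold for any variable with 10 per arm and are not specific to thickness. The sampling error sqrt(2/n) falls as n grows; a systematic difference does not.

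**The case against.** The other side has several good points.

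- **The sentence in Section 2.2 is a statement about risk.** It sits among remarks on sterile conditions and anesthesia, and most naturally means that the study adds no harvest procedure in either arm. A reader might infer that the plan claims equal depth and that the claim is false. The context does not support that reading.
- **The data may exist.** A reader might infer that thickness and location are lost for good. The operative note may well hold them, the photographs may show location, and the case report form is not among the documents. What stands is narrower: the plan does not name these items for collection.
- **The mechanism is inferred.** Nothing says when the operator learns the arm, or why harvest would change with it. A reader might infer that arm-aware harvesting is expected. The documents show only that it is possible.
- **Chance imbalance is not bias.** It is already in the outcome SD and in the standard error, so the 0.30 to 0.75 points should not be read as error on top of it.
- **This is a feasibility study of 20 patients.** That limits the weight of the point. It does not remove it, because a pilot is where the allocation procedure and data form of the later trial are tried out.

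Adjustment alone would also be a poor repair. If knowledge of the arm changed thickness, thickness would be affected by assignment, and conditioning on it could mislead. That objection disappears once the arm is opened after harvest.

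**Conclusion.** The point holds as a cheap improvement. Assignment can be known before harvest in an open-label trial, and the planned data can neither show comparable harvest nor support adjustment for it. These two facts rest on the text alone.

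The size rests on assumptions: with pain SD 2 to 3 and r 0.3 to 0.5, a 0.5 SD difference in thickness corresponds to 0.30 to 0.75 pain points. That is less than one standard error, but not negligible against 2 points. The documents give no basis for saying that such a difference will occur, or in which direction. The gain from the change is one route to bias closed and one source of noise made visible.

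**What to change.** 1. Reconcile Sections 5.1, 6 and 14 so that consent and screening stay where they are and the assignment is opened on Day 0, only after the graft has been taken. The coordinator, who receives the list under Section 5.1, should keep it from the operating team until then. Because blocks are of 2 or 4, the surgeon should also not be given a running tally of past assignments.
2. Add two Day 0 fields in Sections 6 and 14, copied from the operative note: the instrument's thickness setting and the donor-site location. The donor-site row in Section 14 begins at the first follow-up visit, so the Day 0 length and width should be marked there too.
3. Report both items by arm.
4. Pre-specify thickness, then a pre-assignment variable, as a covariate in supportive models for POD 1 pain and for healing. The Wilcoxon and log-rank comparisons stay as they are.

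The cost is two form fields and an assignment opened in the operating room. The product must be at hand for every case; Section 6 already has it available there. Section 7.1 starts adverse event capture at randomization while Section 7.4 starts at consent, so the start point should be stated once when the timing moves. Sample size and endpoint definitions do not change. Time from randomization to healing, as used in Section 9.4, would then start close to the creation of the wound.

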3 RESEARCH OBJECTIVES AND PURPOSE OF THE STUDY

The primary purpose of this study is to assess the feasibility of evaluating the use of a composite collagen, silver-oxidized regenerated cellulose matrix compared to the standard of care dressing on donor site pain for patients undergoing split-thickness skin grafting in preparation for a larger study.

4 STUDY DESIGN AND ENDPOINTS

4.1 Study Description

This is a prospective, randomized, single-center feasibility study. Twenty patients will be randomized into two groups: control and treatment. The control group will receive standard of care (SOC) dressings at the STSG donor site and the treatment group will receive Promogran in direct contact with the donor site in addition to SOC. SOC at NYU Winthrop includes, but is not limited to, xeroform or semiocclusive adhesive dressings. Thrombin spray may be used for hemostasis. Patients are routinely followed in the outpatient wound clinic until wound healing occurs. Healing is defined as complete donor site epithelialization without drainage.

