4.2 Study Endpoints

The primary aim of this feasibility study is to evaluate if using Promogran in addition to SOC will improve the pain score compared to SOC alone. Specifically, we would like to detect a clinically meaningful difference in pain score (≥ 2 points on the pain scale) between the treatment and control arms on postoperative day (POD) 1.

Secondary aims include:

1. Describe and compare the percent of patients healed between treatment groups
2. Describe and compare weekly surface area between treatment groups
3. Compare time to complete donor site healing between treatment groups

4. Describe and compare adverse events between groups
5. Describe and compare decreased use of narcotics and other pain medications between groups
6. Describe and compare percent of granulation tissue at the donor site between treatment groups.
Granulation will be reported in quartiles (0-25%, 26-50%, 51-75%, and 76-100%).

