11.2 Participant and Data Confidentiality

Information about study subjects will be kept confidential and managed according to the requirements of the Health Insurance Portability and Accountability Act of 1996 (HIPAA). Study photos will be kept confidential by not including any identifying features (e.g. patient face, tattoo). De-identifies photos will be kept on the secure NYU Winthrop hospital computer network and only accessed by study personnel.

Those regulations require a signed subject authorization informing the subject of the following:

- What protected health information (PHI) will be collected from subjects in this study
- Who will have access to that information and why
- Who will use or disclose that information
- The rights of a research subject to revoke their authorization for use of their PHI.

In the event that a subject revokes authorization to collect or use PHI, the investigator, by regulation, retains the ability to use all information collected prior to the revocation of subject authorization. For

subjects that have revoked authorization to collect or use PHI, attempts should be made to obtain permission to collect at least vital status (i.e. that the subject is alive) at the end of their scheduled study period.

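### Nothing in the plan keeps the arm from whoever judges closure, drainage and granulation, so the secondary healing endpoints carry observer bias that could be partly avoided

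*Combined protocol and SAP*

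**What the plan says.** - **Masking.** The Methodology row of the Protocol Summary reads "This is a prospective, randomized, open-label, single-center feasibility study". No masking of any person is described.
- **Application.** The Protocol Summary gives the duration of product administration as "One application". Section 6 adds: "Promogran will be available in the operating room and applied by the operating surgeon (study or non-study surgeon) directly to the donor site".
- **Outcome definitions.** Section 4.1: "Healing is defined as complete donor site epithelialization without drainage". Section 4.2 adds granulation, estimated as a percentage and reported in four bands.
- **Assessment.** Section 6: "Dressings will be changed and wounds assessed according to the standard of care at NYU Winthrop Hospital". Photography, length and width are listed for each weekly visit, and Section 14 adds a closure assessment. The one description of an assessor is also in Section 6, for pain after day 10: "pain will be recorded by the assessing clinic provider during the weekly visits".
- **Analysis.** Section 9.4 compares time to healing by Kaplan-Meier and log-rank, and percent healed and granulation by Fisher's exact test.
- **Use of results.** Section 9.1 rules out decisions based on p-values, but treats the observed direction and size of effect as critical to the design of the next trial.

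**The concern.** Three of the six secondary aims in Section 4.2 (percent healed, time to healing, granulation) rest on visual judgment. Whether the last small area of a donor site has closed, or whether a dressing mark counts as drainage, is often a borderline call. Section 2.2 lists faster healing among the expected benefits, so an assessor who knows the arm also knows which way the result is expected to go. Leaning the same way on a few borderline sites would look like a treatment effect.

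An open-label design does not require the wound assessor to know the arm. Here the product is placed once, in the operating room, by a surgeon who may not belong to the study, and later dressing changes follow standard care. Much of the exposure could be reduced at little cost. What is at stake is the credibility of the healing effect sizes that the pilot hands on.

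**Working it through.** The plan gives no figure for healing rates, assessor error or power, so there is no calculation to reproduce. The check has two parts.

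**1. Is the arm kept from the assessor anywhere?**

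| Place | What it provides | Does it mask the wound assessor? |
|---|---|---|
| Section 5.1 | Allocation list goes to the study coordinator | No statement of who is kept from it |
| Section 6 | Wounds assessed under standard care | No assessor named, none independent |
| Section 6, weekly visits | Photographs, length, width | No masked reading planned |
| Section 8 | Coordinator monitors safety; weekly reviews go to the research meeting | No; could spread knowledge of the arm |
| Section 11.2 | "Study photos will be kept confidential by not including any identifying features" | No; this protects privacy |
| Section 12 | Wound Care team keeps the database | No restriction by arm |

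The operating surgeon, who knows the arm, is not excluded from later assessment. The gap is there.

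**2. How large could the effect be?** Every error rate below is an assumption.

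Inputs from the plan: 10 patients per arm (Section 9.1); one visit per week (Section 6); Visit 2 on Day 14 and Visit 3 on Day 28 (Section 14 as printed).

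*Counts.* Let k be the number of treated patients whose call changes because the arm is known.

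- Percent healed, if k unhealed sites are called healed: shift = k/10.
- Mean healing time, if k sites are called closed one weekly visit early: shift = (k/10) × 7 days.
- Fisher's exact p starts from an assumed equal 5/10 against 5/10, with k added to the treated arm.

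| k | Shift in percent healed | Shift in mean healing time | Fisher p |
|---|---|---|---|
| 1 | 10 points | 0.7 days | 1.00 |
| 2 | 20 points | 1.4 days | 0.65 |
| 3 | 30 points | 2.1 days | 0.35 |

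These are two different errors: a site called closed early that does close later changes healing time but not the final percent healed. For one patient the shift in time is 7 days, or 28 − 14 = 14 days between Visits 2 and 3 as printed. The p-values show that the pilot's own test would not flag an error of this size.

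*Rates.* Let p be the true proportion healed in both arms, and f the chance that an unhealed treated site is called healed, with no such error in controls. Then bias = (1 − p) × f.

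| p | f = 0.1 | f = 0.2 | f = 0.3 |
|---|---|---|---|
| 0.3 | 7 points | 14 points | 21 points |
| 0.5 | 5 points | 10 points | 15 points |
| 0.7 | 3 points | 6 points | 9 points |

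*Limit of the mean.* The plan analyses time to healing by Kaplan-Meier and log-rank, and a patient unhealed at the last visit has no observed healing time. The shift in the mean shows scale only; it is not a bias in a planned estimate.

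**The case against.** The strongest reply is that this is an openly declared feasibility pilot of 20 patients, that only secondary endpoints are touched, and that no decision turns on a p-value. The stated purpose concerns donor-site pain, and nothing says the later trial will be sized on healing. All of that stands and limits the severity. It does not remove the point, because Section 9.1 gives weight to observed effects on the outcomes generally.

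A second reply is that masking at these visits cannot be complete. That also stands. Section 7.3 has the clinician who examines the patient judge whether an adverse event is related to the device, and adverse events are recorded at the same weekly visits. The plan does not say how long the sheet stays visible. Patients know their arm. A provider who learns the arm at one visit knows it at every later visit with that patient.

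Some stronger readings are tempting, and the documents do not support them:

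- *That the plan assigns closure and granulation to clinic providers.* The only mention of an assessing provider concerns pain. The rest is inference.
- *That the weekly visit never needs the arm.* Section 7.3 means that it sometimes does.
- *That the photographs are already coded for masked reading.* Section 11.2 describes removal of identifying features, for confidentiality.
- *That the bias could never be repaired.* De-identified photographs are kept, so a later masked reading could recheck epithelialization and granulation, though not fully drainage.

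**Conclusion.** The concern holds as a gap in design: in the text available, nothing keeps the arm from whoever judges closure, drainage and granulation. Percent healed, time to healing and granulation band are exposed to observer bias that could be partly avoided. Severity is minor to moderate.

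The arithmetic that follows from the plan is 10 points on an arm's percent healed per patient called differently, and about 7 days on a patient's healing time per early call (14 days in the one longer interval as printed). How many calls would change is unknown. The range of 1 to 3 in 10, and the 0.7 to 2.1 days that follow, are assumptions, as is the premise that errors run only in favour of treatment. A reader might take 2.1 days as an estimate of the bias; it is not one.

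A reader might also infer that the primary result is compromised by this gap. It is not: POD 1 pain is the patient's own score, and masking the wound assessor would not change it.

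**What to change.** Add one paragraph to Section 6 and one tick-box to the visit form:

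1. Leave the arm off the weekly wound form.
2. The provider already seeing the patient, and where possible not the operating surgeon, records closure, drainage, length, width and granulation and takes the photograph first. This comes before opening any record that shows the arm, and before any judgment of device causality under Section 7.3.
3. The provider ticks whether the arm was known at that visit.
4. Report the tick-box by arm beside the healing results.

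This needs no extra reader or visit and no change in care. The cost is the order of work within the visit and one more item to complete. The limitation is partial masking: the sheet may be visible early on, patients may mention their arm, adverse event causality and the weekly safety review can reveal it, and a provider once unmasked stays so for that patient. The tick-box shows how often this happened, which also tells the next trial whether masked wound assessment is workable.
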